The primary aim of this observational prospective study is to evaluate, whether there is a difference in the blood flow, calculated as PI and RI in the arteriae uterinae right / left between women, undergoing HRT- or NC-cycle for FET. Measurements on the day of cycle start and the day of progesterone rise in NC-cycles / start of progesterone administration in HRT-cycles (+/- 1 - 2 days) will be performed.

Secondary Objectives/research questions

- To evaluate differences (delta) between the mean PI (between right and left A. uterine) and mean RI (between right and left A. uterine) on the day of cycle start and the day of ovulation induction - 1 - 2 days
- To compare thickness of the lining between HRT or NC.
- To compare number of days of estradiol exposure before the embryo transfer between HRT or NC.

Introduction

A. Background:

A wide spectrum of different factors, including uterine receptivity and endometrial thickness (Abdalla et al, 1994; Noyes et al, 1995) and endometrial texture (Bakos et al, 1993), have been implicated as crucial factors in implantation. It has also been suggested that uterine receptivity is related to the uterine blood flow. Due to the availability of ultrasound Doppler measurements, the uterine blood flow can be assessed non-invasively by transvaginal Doppler ultrasonography.

It is also known, that there are remarkable differences in the endocrinological milieu between natural cycles, ovarian stimulation cycles for IVF / ICSI and hormonal replacement cycles. Those differences may lead to different flow pattern in the vessels, providing blood supply to the uterus.

Until now, there are no data whether there is a difference in the blood flow of the aa. Uterinae .

B. Justification:

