- Intake of Aspirin or similar medication which might influence the blood flow
- Status after tubal ligation
- Status after surgery in the adnexal region on 1 side

E. Intervention and Follow-up

- Patient will present themselves on day 2 / 3 of their period.

- Patients will undergo ovarian stimulation for IVF / ICSI in a GnRH-antagonist protocol: Start of stimulation medication (HMG, recFSH) on either day 2 or 3 of the cycle, dosage according to the ovarian response. From day 5 of stimulation a GnRH-antagonist will be added to prevent premature ovulation. Medication for ovulation induction (hCG, GnRH-agonist or dual trigger) will be given when at least 3 follicles are ≥ 17 mm.
- Patients will be planned for FET in either HRT or NC, according to the physician's decision.
- Factors to recommend HRT FET: irregular cycle, PCO, unavailability for treatment monitoring
- Factors to recommend NC FET: regular cycle 28 -33 days, availability for treatment monitoring

Endometrial preparation approaches:**Artificial (HRT) Cycles:**

- Commence E2 4mg from day 2/3 of period for 3 days
- Increase E2 to 6mg on day 4 of E2 treatment. E2 dose may be increased according to clinician discretion based on endometrial thickness.
- The patient will be scanned transvaginally throughout the HRT cycle to not only monitor endometrial development but to also exclude the presence of a dominant follicle on the ovaries.
- In conjunction with ultrasound monitoring the patient will undergo serial measurements of serum LH, estradiol and progesterone levels.
- Commence the initial progesterone dose of 100mg at 22hrs (vaginal suppository) after ≥ 10 days and ≤ 16 days of estradiol administration when the minimal endometrial thickness achieved is 6mm with a trilaminar appearance.
- Subsequently increase progesterone administration to 100mg vaginally three times daily. Continue estradiol administration 6mg (3 tablets daily). Embryo transfer is scheduled 5 days following the initial initiation of progesterone

Spontaneous natural cycles:

- Commencing on the second day of menses and intermittently throughout the patients' natural cycle ultrasound scans will be performed to monitor follicular growth.

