- In conjunction with ultrasound monitoring the patient will undergo serial measurements of serum LH, estradiol and progesterone levels to accurately determine the timing of ovulation. These serum hormonal levels will be measured with an automated Elecsys® immunoanalyzer (Roche Diagnostics, Mannheim, Germany).
- The LH surge will be considered to have begun when the concentration rises by 180% above the most recent serum value and continues to rise thereafter (Irani et al. 2017, Fatemi et al., 2010).
- Day 1 after the LH rise, a decrease in estradiol concentration is identified. Twenty four hours later progesterone concentrations rise with a level of greater than or equal to 1.5nmol /L confirming ovulation (day 0) (Irani et al., 2017; Speroff et al.). This is considered as day 0 with initiation of vaginal progesterone 100mg (vaginal suppository) at 22pm that night. The following day (day 1) the patient increases progesterone administration to 100mg vaginally three times daily (8 hourly) and continues this regime until 7 weeks gestation as per clinic protocol. Embryo transfer is scheduled 5 days (day 5) following confirmation of ovulation (day 0).

For all study arms, transvaginal scan will be performed after the patient had emptied the bladder and is positioned in lithotomic position.

Measurement of the Doppler in the aa. uterinae:

A sagittal section of the uterus will be obtained and the cervical canal and internal cervical os will be identified. The transducer will be gently tilted from side to side and color flow mapping will be used to identify each uterine artery along the side of the cervix and uterus at the level of the internal os. Pulsed wave Doppler will be used with the sampling gate set at 2 mm to cover the whole vessel and care will be taken to ensure that the angle of insonation is less than 30°. When three similar consecutive waveforms are obtained, the PI and peak systolic velocity (PSV) will be measured and the mean PI of the left and right arteries calculated.

Images of the blood flow measurements will be taken and stored in an access-restricted folder. After completion of the study recruitment and data analysis, the images will be destroyed.

Timing for measurement of the Doppler in the aa. Uterinae will be performed:

- Ovarian stimulation cycle: day 2 or 3 of the cycle; day of ovulation induction or 1 to 2 days before in case patient will not be seen directly on the day of ovulation induction
- FET cycle:

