- HRT: day 2 or 3 of the cycle and day of start of progesterone administration or 1 to 2 days before in case patient will not be seen directly on the day when she starts progesterone
- NC: day 2 or 3 of the cycle and day of start of progesterone rise or 1 to 2 days before in case patient will not be seen directly on the day when progesterone starts to rise

F. Collection of biological samples and information

No biological samples will be collected for this study

Statistical methodology

A. Data base

The database will be rigorously defined with the variables destined to be analyzed according to the objectives set. The necessary information will be exported from the clinical information manager, SIVIS, to a table in Excel format through a database-based query system. The data which is not recorded in SIVIS will be collected in a password-coded EXCEL file to guarantee the data protection.

The exported data will be duly codified in order to protect the clinical and personal information of the patients according to the applicable law in the place where the research project is carried out.

Finally, and prior to the statistical study, an exploratory data analysis will be carried out to review the quality of the information extracted.

B. Study Variables

EXPOSURE VARIABLES (INDEPENDENT)

- Type of endometrial stimulation. Categorical dichotomous variable (HRT or natural cycle)

MAIN-OUTCOME MEASURE (DEPENDENT)

- Difference in the blood flow, calculated as PI and RI, between the HRT- and the NC-FET cycles, on the day of progesterone administration / progesterone rise. Quantitative continuous variable

SECONDARY OUTCOME MEASURES (DEPENDENT)

- δ_{S11} : Continuous quantitative variable measured as the differences between average PI value on the day of cycle start and the day of ovulation induction - 1 - 2 days.
- δ_{S12} : Continuous quantitative variable measured as the differences between average RI value on the day of cycle start and the day of ovulation induction - 1 - 2 days.
- Thickness of the lining. Continuous quantitative variable measured in millimeters (mm).
- Number of days of estradiol exposure before the embryo transfer. Discrete quantitative variable.

CONTROL VARIABLES

- Cycles days before start of progesterone administration.
- In HRT cycles: amount (mg) of administered Estradiol.
- Age of the patient
- BMI of the patient
- Number of previous pregnancies
- Number of previous C-sections
- Number of previous miscarriages

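### Doppler PI/RI on day 2/3 of the FET cycle is scheduled in both groups but has no role in the HRT-NC comparison; report it by group and add a baseline-adjusted difference beside the planned one

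*Combined protocol and SAP*

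**What the plan says.** **Measurement.** Under the main objective, the combined protocol and SAP names two Doppler days in the FET cycle: "Measurements on the day of cycle start and the day of progesterone rise in NC-cycles / start of progesterone administration in HRT-cycles". Section E (Intervention and Follow-up) schedules both in each group: "HRT: day 2 or 3 of the cycle and day of start of progesterone administration" and "NC: day 2 or 3 of the cycle and day of start of progesterone rise", with a margin of one or two days before the second.

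**Outcome.** Section B (Study Variables) defines the main outcome as the difference in PI and RI "between the HRT- and the NC-FET cycles, on the day of progesterone administration / progesterone rise". The only change variables are secondary, such as the "differences between average PI value on the day of cycle start and the day of ovulation induction". In the Doppler timetable of section E, ovulation induction occurs only in the ovarian stimulation cycle, so these deltas do not use the FET-cycle day 2/3 value.

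**Control variables.** The list in section B covers cycle days before progesterone, estradiol amount, age, BMI, obstetric history and smoking. It does not include PI or RI on day 2/3. The homogeneity analysis in section D is limited to the listed control variables.

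**Analysis.** Objective Assessment in section D plans 90%, 95% and 99% intervals for each group and for the difference, with a t-test or a non-parametric test given as indicative. No covariate is named.

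**Allocation.** The physician decides between HRT and NC. The stated grounds include: "Factors to recommend HRT FET: irregular cycle, PCO, unavailability for treatment monitoring".

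**The concern.** A same-cycle measurement of the outcome variable, taken at about the start of preparation, is collected in every patient and then given no part in the comparison. In a randomised study this would cost only precision. Here the groups are formed on clinical grounds, and the Homogeneity Analysis section itself recognises that a group difference may come from something other than the preparation. Irregular cycles or PCO might go with a different uterine artery PI before any preparation begins. The planned analysis would neither show nor account for such a difference.

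The interval for the HRT-NC difference is the main product of this pilot, and the Justification says that a negative influence of one approach should be taken into account in future choices. A reader of that interval should be able to see whether the groups already differed at cycle start.

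**Working it through.** **Inputs from the documents.** Sample Size plans 30 patients per arm. It estimates about 80 patients in total and adds 5% for losses: 80 x 1.05 = 84, as stated. No SD, effect size or correlation is given, so everything below is in SD units of the progesterone-day value.

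**Assumptions.**
- rho: correlation between day 2/3 and the progesterone day, 0.3 / 0.5 / 0.7.
- d: true HRT-NC difference on day 2/3, 0 or 0.5 SD.
- k: share of d that would still be present on the progesterone day with no preparation effect; 0 (none), rho, or 1 (all).
- Equal SDs on the two days.

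**Step 1. Precision, 95% half-width of the difference.**
- Unadjusted: t(0.975, 58) x sqrt(2/30) = 2.002 x 0.2582 = 0.517.
- Adjusted for day 2/3: t(0.975, 57) x sqrt[(1 - rho²)(2/30 + d²/58)].

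| | rho 0.3 | rho 0.5 | rho 0.7 |
|---|---|---|---|
| Adjusted, d = 0 | 0.493 | 0.448 | 0.369 |
| Adjusted, d = 0.5 | 0.509 | 0.462 | 0.381 |
| Change from day 2/3: 0.517 x sqrt[2(1 - rho)] | 0.612 | 0.517 | 0.400 |

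The equivalent gain in patients, (2/30) / [(1 - rho²)(2/30 + d²/58)] - 1, is 10 / 33 / 96% at d = 0 and 3 / 25 / 84% at d = 0.5. The change score is less precise than the unadjusted comparison when rho is below 0.5.

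**Step 2. Bias when there is no preparation effect.**
- Unadjusted: k x d.
- Adjusted: (k - rho) x d.
- Change: (k - 1) x d.

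The unadjusted and adjusted biases are equal in size at k = rho/2, so adjustment reduces bias only if k exceeds rho/2.

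**Step 3. Coverage of the nominal 95% interval at d = 0.5** (simulation, 20,000 runs per cell, 30 per arm; % at rho 0.3 / 0.5 / 0.7).

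| | Unadjusted | Adjusted | Change |
|---|---|---|---|
| k = 0 | 95 / 95 / 95 | 91 / 81 / 57 | 64 / 52 / 31 |
| k = rho | 91 / 84 / 74 | 95 / 95 / 95 | 80 / 84 / 89 |
| k = 1 | 52 / 52 / 52 | 73 / 82 / 88 | 95 / 95 / 95 |

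Each estimate is right under one assumption and wrong under the others. The documents do not say which applies.

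**Step 4. Can a baseline test decide?** A two-sided 5% t-test on day 2/3 with 30 per arm has 48% power for a 0.5 SD difference and 16% for 0.25 SD. A non-significant result would therefore be weak evidence that the groups started level.

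**The case against.** The strongest reply is that the plan is complete as it stands. Objective Assessment says that it addresses the primary objective, and Study Variables fixes that outcome on the progesterone day. Read together, they give a definite day and a definite unadjusted analysis. That stands. A reader might infer that the primary day is undefined, or that the analyst is free to choose among unadjusted, adjusted and change estimates after seeing the data. The documents support neither: the objective paragraph lists measurement days without redefining the outcome, and an adjusted or change analysis would depart from the plan.

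A second reply is that adjustment is not clearly better. This also stands. At k = 0 and d = 0.5 the adjusted interval covers about 91 / 81 / 57%, against 95% unadjusted. One might infer that the adjusted estimate should lead, but nothing in the documents settles how far an early difference persists.

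A third reply is that the day 2/3 value may not be a clean baseline in HRT patients, because estradiol starts at the same time: "Commence E2 4mg from day 2/3 of period for 3 days". The documents do not give the order of scan and first dose. It cannot be inferred that any scan follows treatment, and this does not justify an extra subset analysis.

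The descriptive summary might include day 2/3 values, but that gives them no specified part in the comparison. Finally, the measurement procedure states that "the PI and peak systolic velocity (PSV) will be measured and the mean PI of the left and right arteries calculated" and omits RI, although the abstract, the aim and the outcomes all name RI. That is a separate wording point.

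**Conclusion.** The point holds as an unused baseline. FET-cycle day 2/3 PI and RI are scheduled in both groups and named under the main objective, but have no role in the HRT-NC comparison, in a cohort where the physician chooses the group.

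The size depends on quantities that the documents do not give. If the groups start level, adjustment shortens the 95% half-width by about 5%, 13% or 29% at rho 0.3, 0.5 or 0.7 (0.493, 0.448 or 0.369 divided by 0.517). If they start 0.5 SD apart, the unadjusted difference carries a bias between 0 and 0.5 SD as k runs from 0 to 1. The plan as written would give no sign of this.

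The consequence falls on the estimate and its interval, since the test is only indicative. The planned analysis remains a legitimate one and should stay. All figures assume 30 per arm; the plan expects 2:1 recruitment, and at 53 and 27 patients the unadjusted half-width would be 0.471 SD. This is a modest improvement to a descriptive pilot.

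**What to change.** 1. In Study Variables, add FET-cycle day 2/3 PI and RI to the control variables. Report them by group, with the difference and its interval. Do not let a significance test on them decide whether to adjust.
2. In Objective Assessment, keep the planned unadjusted progesterone-day difference. Pre-specify beside it the difference from a linear model with the same-cycle day 2/3 value as covariate, with the same 90%, 95% and 99% intervals, for PI and for RI. The change from day 2/3 may be shown as a further descriptive estimate.
3. State that these estimates rest on different assumptions about how far a day 2/3 difference persists, and that none of them removes the clinical selection factors that decide between HRT and NC.

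**Cost.** Some SAP wording and one degree of freedom per model; no new visit or scan. The downside is a bias of size rho x d in the adjusted estimate if a day 2/3 difference would not have persisted: 0.15, 0.25 or 0.35 SD at d = 0.5 and rho 0.3, 0.5 or 0.7. That is why the unadjusted estimate stays in the report.

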Until now, the changes in the blood flow of the aa. uterinae during hormonal stimulation for IVF / ICSI as well as during the preparation for FET are unclear. Additionally, the "best" approach to prepare the endometrium and further on to perform a frozen embryo transfer is still not clear and the data are contradictory. This study will evaluate whether there is any change in blood flow during hormonal stimulation for IVF/ICSI and during different types of endometrial preparation for FET. In case this study would show that the blood flow of the arteria uterina right and left is influenced negatively by one of the approaches, used for endometrial preparation of the FET, then this should be taken into account in future when deciding for one or the other approach.

Methodology

A. Study Design

- Prospective cohort study, observational and unicentric (in IVIRMA Middle East Fertility Clinic, Abu Dhabi, UAE).

B. Study period and context

- Patients who are treated for primary / secondary infertility in IVIRMA Middle East Fertility Clinic, Abu Dhabi, UAE
- Estimated study duration: 6 - 8 month
- Study would start after approval of the study protocol by EC of IVIRMA Middle East Fertility Clinic Abu Dhabi.
- Study would end after inclusion of the number of patients, estimated due to the sample size calculation

C. Reference Population

Pat. with primary / secondary infertility, who undergo an ovarian stimulation treatment for IVF/ICSI and subsequently are planned for FET with vitrified embryos, either as HRT-FET or as NC-FET

D. Subject Inclusion/exclusion criteria

Inclusion criteria:

- Patients who undergo ovarian stimulation in a GnRH-antagonist protocol for IVF / ICSI
- Patients who have vitrified embryo(s)
- Preparation for FET either in HRT or NC cycle

Exclusion criteria:

- Poor responder according to Bologna criteria (Ferraretti et al.) as follows:
- At least two of the following three features must be present:
 - (i) Advanced maternal age (≥ 40 years) or any other risk factor for POR;
 - (ii) A previous POR (≤ 3 oocytes with a conventional stimulation protocol);
 - (iii) An abnormal ovarian reserve test (i.e. AFC, 5–7 follicles or AMH, 0.5 –1.1 ng/ml).
- Uterine surgery for removal of fibroids (hysteroscopic, laparoscopic) or removal of uterine septum
- Endometriosis
- Asherman-Syndrome
- Previous cytotoxic treatment
- Previous radiation of the uterus / adnexal region
- Known hypertension

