- Smoker status: Smoking yes/no

C. Sample Size

So far, no study has been published evaluating the PI and RI of the arteria uterina between HRT- and NC-FETs.

The study of *Tekay et al.* compared the PI of the arteria uterina in a total of 57 patients in fresh ET's after ovarian stimulation and FET with HRT-preparation of the endometrium. However, this article does not study all the variables of our interest. Besides, it has low statistical power and our populations are different, so we consider that it is more convenient to carry out a pilot study to study descriptively the variables of interest in our population.

As this will be a pilot study, we plan to include 30 patients in each arm (HRT / NC), therefore we would estimate that we will have to include approximately 80 patients in total, as at the time of ovarian stimulation it will not be clear which type of FET patient will undergo later on. This approach was chosen in order not to interrupt patient recruitment. As this is expected to be a 2 : 1 recruitment (HRT : NC), an intra-group homogeneity analysis will be performed and if there are differences, patients from this group will be randomly selected for statistical analysis. Besides, in anticipation of potential participants wishing to withdraw from the study, an additional 5% of patients to the total sample will be added to cover possible losses, recruiting a total of 84 participants.

D. Statistical data analysis

EXPLORATORY DATA ANALYSIS

A statistical summary of the data collected in the study describing patient's population, cycle's most relevant parameters together with clinical results will be provided.

- Categorical variables will be presented in frequency tables, providing absolute frequencies and proportion of each level of each factor in the sample.
- Continuous variables will be summarized according the mean, standard deviation and 95%-confidence interval, all of them will be represented by diagrams or densities quartiles.

Exploratory data analysis will allow evaluating data quality and detecting anomalies.

HOMOGENEITY ANALYSIS

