Although the inclusion criteria and study design tend to preserve the homogeneity of study, it is important to ensure comparability between groups for each control variable. Since each patient is assigned to a group according to clinical criteria and not by random assignment between groups, it will be important to perform a homogeneity analysis to ensure that the effect studied may be due to the type of endometrial preparation and not to the effect that may be caused by a control variable behaving differently between the two study groups.

Consequently, categorical variables will be compared using the χ^2 test, and for quantitative variables, a t-Student test will be applied (if we can assume normality, if it is not possible, we will use the Kruskal-Wallis test).

OBJECTIVE ASSESSMENT

To assess the primary objective, and considering the descriptive nature of any pilot study, confidence intervals of 90%, 95% and 99% will be provided for the blood flow level in each group, and for the difference

between the comparison groups. A basic comparison test will also be provided on an indicative basis. In order to do this, and considering the size of the sample, we will first apply tests of the normality of the data. If these tests are favourable, a t-Student test will be applied. In case of not being able to assume normality, we will apply a non-parametric test.

We will proceed in the same way for the rest of the secondary objectives.

Work plan

Phase I: drafting of protocol ([name], [name], [name]) and review / approval through UAGI and EC approval

Phase II: Patient recruitment and follow-up ([name], [name])

Phase III: Data analysis ([name], designated statistician from UAGI)

Phase IV: Drafting and reviewing of manuscript, submission and publication ([name], [name], [name], [name], [name])

	2019											
	Jan	Feb	Mar	Apr	May	Jun	Jul	Aug	Sep	Oct	Nov	Dec
Phase I												
Phase II												
Phase III												
Phase IV												
Phase V												

	2020											
	Jan	Feb	Mar	Apr	May	Jun	Jul	Aug	Sep	Oct	Nov	Dec
Phase I												
Phase II												
Phase III												
Phase IV												
Phase V												

Ethical issues

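### The plan's 30 patients per arm do not follow from its own total and split: 80 patients (84 recruited) at 2:1 give about 53 HRT and 27 NC.

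*Combined protocol and SAP*

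**What the plan says.** All the figures stand in one paragraph of the combined protocol and SAP (Statistical methodology, C. Sample Size).

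- Target per arm: "we plan to include 30 patients in each arm (HRT / NC").
- Total: "therefore we would estimate that we will have to include approximately 80 patients in total". The reason given is that the type of FET is not yet known when patients enter at ovarian stimulation.
- Split: "As this is expected to be a 2 : 1 recruitment (HRT : NC").
- Recruited: 5% is added for participants who withdraw, "recruiting a total of 84 participants".
- Unequal groups: after a homogeneity analysis, "if there are differences, patients from this group will be randomly selected for statistical analysis". No number to select down to is given.

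Three other places bear on the point.

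- Methodology, B. Study period and context: "Study would end after inclusion of the number of patients, estimated due to the sample size calculation".
- Methodology, E. Intervention and Follow-up: "Patients will be planned for FET in either HRT or NC, according to the physician's decision".
- Statistical data analysis, Objective assessment: "confidence intervals of 90%, 95% and 99% will be provided for the blood flow level in each group, and for the difference" between them.

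**The concern.** The plan gives no power, effect size or SD. That is acceptable for a descriptive pilot, but it leaves 30 as the only per-arm target. The total and the split should therefore produce it, and in the NC arm they do not.

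Nothing else in the plan makes up the gap. The physician decides the type of FET, recruitment ends at the calculated number, and no NC quota or minimum is stated. Random selection can shrink the HRT group but cannot add NC patients.

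At stake is whether the stated NC number, and the precision a reader would take from it, will be met. The HRT arm is not in question, since it comfortably exceeds 30.

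**Working it through.** **Inputs, all from the Sample Size section:** 30 per arm; about 80 in total; HRT:NC of 2:1, so an NC share of 1/3; 5% added for withdrawals; 84 recruited.

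**1. From 80 to 84.** 80 × 1.05 = 84. This step reproduces.

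**2. From 30 per arm to 80.** At 2:1, 30 NC need 30 × 3 = 90 patients (60 HRT, 30 NC). This step does not reproduce: 80 is 10 short.

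**3. What the stated totals give at 2:1.**

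| Patients | HRT | NC |
|---|---|---|
| 80 | 53.3 | 26.7 |
| 84, no loss | 56 | 28 |
| 84 after 5% loss (84 × 0.95 = 79.8) | 53.2 | 26.6 |

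For 80 patients to contain 30 NC, the split must be 50:30, which is 1.67:1 (NC share 37.5%).

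**4. Chance of at least 30 NC.** This assumes independent assignment, so that the NC count is binomial. With 5% loss, the probability per recruit is 0.95 × NC share.

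| Patients | NC share | P(NC ≥ 30) |
|---|---|---|
| 80 evaluable | 1/3 | 0.249 |
| 84, no loss | 1/3 | 0.360 |
| 84, 5% loss | 1/3 | 0.246 |
| 84, 5% loss | 30% (assumed) | 0.091 |
| 84, 5% loss | 37.5% (assumed) | 0.534 |
| 84, 5% loss | 40% (assumed) | 0.704 |

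**5. NC group's own 95% interval.** Half-width in SD units = t(0.975, n−1)/√n.

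- n = 30: 2.045/5.477 = 0.373
- n = 27: 2.056/5.196 = 0.396

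**6. 95% interval for the difference, common SD assumed.** Half-width = t(0.975, n₁+n₂−2) × √(1/n₁ + 1/n₂).

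| HRT:NC | Half-width (SD) |
|---|---|
| 30:30 | 2.002 × 0.258 = 0.517 |
| 53:27, all analysed | 1.991 × 0.236 = 0.471 |
| 30:27, HRT cut to 30 | 2.004 × 0.265 = 0.532 |
| 27:27, HRT cut to 27 | 2.007 × 0.272 = 0.546 |

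**7. The same with unequal SDs (Welch interval).** Units are the HRT SD; the SD ratios are assumptions, because the plan gives no SD.

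| NC SD / HRT SD | 30:30 | 53:27 |
|---|---|---|
| 0.75 | 0.458 | 0.398 |
| 1.5 | 0.661 | 0.647 |
| 2 | 0.824 | 0.832 |

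Only at a ratio of about 2 does 53:27 become wider, and then marginally.

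**The case against.** **The inputs are soft.** The total is approximate and the ratio an expectation; 1.67:1 could loosely be called 2:1, and then 80 would be right. It is true that the 25% depends on an NC share of exactly one third, which is why the range of 9% to 70% is shown. But the ratio written down is 2:1, a gap of 10 in 80 is more than rounding, and the paragraph ends on a firm 84. With no loss, 84 patients do give 28 NC, but only by spending the allowance set aside for withdrawals.

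**Recruitment might continue until both arms are full.** The end-of-study sentence refers to the sample size calculation, which also contains 30 per arm, so it does not strictly exclude this. The likelier reading is the stated total of 84, and no section says that recruitment goes on until NC reaches 30.

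**It is a pilot.** This stands. The tests are offered only as indicative, so the point is of low severity.

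**Stronger readings that the documents do not support.** A reader might infer that the primary comparison loses precision or is underpowered. The plan claims no power, and with similar SDs and everyone analysed, 53:27 is slightly more precise for the difference than 30:30. A reader might also infer that the random-selection sentence should simply be struck out. That sentence is the plan's only stated response to differences found in the homogeneity analysis, so removing it is a separate question about the analysis.

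**Conclusion.** The point holds at low severity. The three statements (30 per arm, about 80 in total, 2:1) cannot all be true. On the plan's own figures the NC arm is expected to reach about 27, roughly 3 short of 30.

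The one clear cost is in the NC group's own interval, about 0.40 SD against 0.37 SD. The interval for the difference is no wider than at 30:30 when all patients are analysed and SDs are similar (0.47 against 0.52 SD with a common SD). It is marginally wider if the NC SD is about twice the HRT SD (0.83 against 0.82 HRT SD).

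The expected counts assume the stated 2:1 split and no attrition beyond the 5%. That 5% covers withdrawals only. Patients enter at ovarian stimulation, and some may never reach FET; the plan gives no rate for this. Purely as an assumption, total loss of 10% to 20% would leave 84 × 0.90/3 = 25.2 to 84 × 0.80/3 = 22.4 NC. So 27 is itself an optimistic figure.

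**What to change.** In the Sample Size section, replace the 30-per-arm statement with wording such as:

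> 84 recruited; at the expected 2:1 split and after 5% withdrawal, about 53 HRT and 27 NC are expected, fewer if some patients enrolled at ovarian stimulation do not reach FET. The expected 95% CI half-width is about 0.40 SD for the NC group and, with all patients analysed and a common SD, about 0.47 SD for the difference.

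Add that patients are not removed merely to equalise group sizes, since cutting HRT to 30 or 27 only widens the interval for the difference (0.53 or 0.55 SD). How to respond to differences found in the homogeneity analysis is a separate issue and is left untouched here.

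The cost is rewording one paragraph, with no added patients; the stated NC number falls from 30 to about 27.

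If 30 NC is to remain a firm figure, the end of recruitment has to be tied to the NC count. With a 1/3 NC share, 5% loss and no other attrition, that means 30/(0.95/3) = 94.7, about 95 recruited on average, and up to 114 in 90% of cases. A fixed total of 90 evaluable would reach 30 NC only about 54% of the time.
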